3.4.2. Study Drug Discontinuation Considerations

The Medical Monitor should be consulted prior to study drug discontinuation whenever feasible.

Study medication should be permanently discontinued in the following instances:

- Any opportunistic infection
- Any serious infection that requires antimicrobial therapy or hospitalization, or any infection that meets SAE reporting criteria.
- Complicated herpes zoster infection (with multi-dermatomal, disseminated, ophthalmic, or CNS involvement)
- Unacceptable toxicity, or toxicity that, in the judgment of the investigator, compromises the subject's ability to continue study-specific procedures or is not considered to be in the subject's best interest
- Need for prohibited concomitant medication (see Section 5.8)

- Subject request to discontinue for any reason
 - Subject noncompliance, as per judgment of investigator
 - Request from Gilead, a regulatory agency or an IRB or IEC
 - Female subject becomes pregnant during the study; refer to Section 7.7.2.1
 - Positive HCV VL
 - Investigator discretion
 - Laboratory criteria:
After becoming aware of any of the below described abnormal laboratory values at any time, an unscheduled visit should occur within 3 to 7 days, with the exception of creatinine clearance which should be retested within 7 to 14 days. Retest may be obtained sooner if medically indicated per investigator judgment. If the laboratory abnormality is confirmed by the retest, then study medication should be discontinued and further care of the subject should be directed per the investigator.
 - total white blood cell (WBC) count < 2000 cells/mm³ (SI: < 2.0x10⁹ cells/L)
 - neutrophil count < 1000 neutrophils/mm³ (SI: < 1.0x10⁹ cells/L)
 - hemoglobin < 8.0 g/dL (SI: < 80 g/L)
 - platelet count < 75,000 platelets/mm³ (SI: < 75.0x10⁹ cells/L)
 - AST or ALT elevation:
 - > 3xULN with at least 1 total bilirubin value >2xULN
 - > 3xULN with elevated international normalized ratio (INR)
 - > 5xULN, regardless of total bilirubin or accompanying symptoms
- Note:** For the above described AST or ALT elevations, additional investigations (such as: review of ethanol, recreational drug use, dietary supplement consumption; testing for acute hepatitis A, B or C infection and biliary tract imaging) should be promptly considered by the investigator; these subjects should be discussed with the study Medical Monitor.
- estimated creatinine clearance < 40 mL/min based on the Cockcroft-Gault formula

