3.2. Subject Grouping

For the analysis of placebo-controlled period (up to week 24), subjects will be presented by four treatment groups:

- Filgotinib 200 mg
- Lanraplenib 30 mg
- Tirabrutinib 40 mg
- Placebo

For the analyses of the entire study period, subjects will be grouped into seven treatment groups as specified in Table 1. For the analyses based on the FAS Analysis Set, subjects will be grouped according to the treatment to which they were randomized at Study Day 1 and Week 24. For the analyses based on the Safety Analysis Set, subjects will be grouped according to the actual treatment that they received. The actual treatment received will differ from the randomized treatment only when their actual treatment differs from randomized treatment for the entire treatment duration.

Table 1. Treatment Groups for the Entire Study Summaries

Filgotinib 200 mg	Filgotinib 200 mg from Study Day 1
Lanraplenib 30 mg	Lanraplenib 30 mg from Study Day 1
Tirabrutinib 40 mg	Tirabrutinib 40 mg from Study Day 1
Placebo/Filgotinib 200 mg	Placebo up to Week 24 and Filgotinib 200 mg after Week 24 first dose
Placebo/Lanraplenib 30 mg	Placebo up to Week 24 and Lanraplenib 30 mg after Week 24 first dose
Placebo/Tirabrutinib 40 mg	Placebo up to Week 24 and Tirabrutinib 40 mg after Week 24 first dose
Placebo	Placebo group with study drug withdrawn prior to or at Week 24 (not received drug assigned at Week 24)

For the PK Analysis Set, subjects will be grouped according to the actual treatment they received.

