7. SAFETY ANALYSES

The safety analyses will be performed for the placebo-controlled treatment period up to Week 24, and for the entire study duration. Analyses for these periods will be presented by the treatment groups specified in Section 3.

For the analyses of adverse events (AEs) that include data after Week 24 the exposure-adjusted analyses will be presented.

For the AEs, laboratory results and concomitant medication data, the collection/start date will be used to determine which reporting period the record belongs to. For other parameters collected on CRFs, the nominal visits will be used.

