7.1.5. Treatment-Emergent Adverse Events

7.1.5.1. Definition of Treatment-Emergent Adverse Events

Treatment-emergent adverse events (TEAEs) of the entire study duration are defined as 1 or both of the following:

- Any AEs with an onset date on or after any study drug start date and no later than 30 days after permanent discontinuation of any study drug
- Any AEs leading to premature discontinuation of study drug.

TEAEs up to Week 24 are defined as 1 or both of the following:

- Any AEs with an onset date on or after Day 1 and no later than the day before the Week 24 treatment start date.
- For subjects who discontinued treatment prior to Week 24 visit, any AEs with an onset date no later than 30 days after permanent discontinuation of study drug

TEAEs of active treatment are defined similarly as the definition of the entire study duration, except that active study drug instead of any study drug will be used:

- Any AEs with an onset date on or after the first dose of active study drug and no later than 30 days after permanent discontinuation of active study drug.

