7.2. Laboratory Evaluations

Laboratory data collected during the study will be analyzed and summarized using both quantitative and qualitative methods. Summaries of laboratory data will be provided for the Safety Analysis Set and will include data collected up to the last dose of study drug plus 30 days for subjects who have permanently discontinued study drug, or all available data at the time of the database snapshot for subjects who were ongoing at the time of an interim analysis. The analysis will be based on values reported in conventional units. When values are below the LOQ, they will be listed as such, and the closest imputed value will be used for the purpose of calculating summary statistics as specified in Section 3.7. Hemolyzed test results will not be included in the analysis, but they will be listed in by-subject laboratory listings.

A baseline laboratory value for the placebo-controlled and entire study period will be defined as the last nonmissing measurement obtained on or prior to the date/time of first dose of any study drug. For the active treatment period, the baseline for the subjects originally randomized to placebo will be the latest measurement before or on the day when the first dose of active study treatment is administered.

A by-subject listing for laboratory test results will be provided by subject ID number and visit in chronological order for hematology, serum chemistry, and urinalysis separately. Values falling outside of the relevant reference range and/or having a severity grade of 1 or higher on the CTCAE severity grade will be flagged in the data listings, as appropriate.

No formal statistical testing is planned.

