7.2.3. Liver-related Laboratory Evaluations

Liver-related abnormalities after initial study drug dosing will be examined and summarized using the number and percentage of subjects who were reported to have the following laboratory test values for postbaseline measurements:

- Aspartate aminotransferase (AST): (a) > 3 times of the upper limit of reference range (ULN); (b) > 5 x ULN; (c) > 10 x ULN; (d) > 20 x ULN
- Alanine aminotransferase (ALT): (a) > 3 x ULN; (b) > 5 x ULN; (c) > 10 x ULN; (d) > 20 x ULN
- AST or ALT: (a) > 3 x ULN; (b) > 5 x ULN; (c) > 10 x ULN; (d) > 20 x ULN
- Total bilirubin: > 2 x ULN
- Alkaline phosphatase (ALP) > 1.5 x ULN
- AST or ALT > 3 x ULN and total bilirubin: (a) > 1.5 x ULN; (b) > 2 x ULN

The summary will include data from all postbaseline visits on active treatment up to 30 days after the last dose of study drug. For individual laboratory tests, subjects will be counted once based on the most severe postbaseline values. For both the composite endpoint of AST or ALT and total bilirubin, subjects will be counted once when the criteria are met at the same postbaseline visit date. The denominator is the number of subjects in the Safety Analysis Set who have nonmissing postbaseline values of all relevant tests at the same postbaseline visit date.

The analyses will be presented for the placebo-controlled period and entire study period.

A listing of subjects who met at least 1 of the above criteria will be provided.

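### SAP 7.2.3: limiting the liver table to active treatment contradicts its own placebo-controlled presentation, and the same-date rule leaves some transaminase–bilirubin cases out of the joint count

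*SAP*

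**What the plan says.** SAP 7.2.3 tabulates subjects whose AST, ALT, bilirubin or alkaline phosphatase exceeds set multiples of ULN, plus a composite of AST or ALT >3xULN with total bilirubin >1.5xULN or >2xULN. Its data rule is: "The summary will include data from all postbaseline visits on active treatment up to 30 days after the last dose of study drug". Later in the section: "The analyses will be presented for the placebo-controlled period and entire study period".

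SAP 7 says of these two periods: "Analyses for these periods will be presented by the treatment groups specified in Section 3". SAP 3.2 then states: "For the analysis of placebo-controlled period (up to week 24), subjects will be presented by four treatment groups". The fourth of those groups is Placebo.

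For the composite, SAP 7.2.3 states that "subjects will be counted once when the criteria are met at the same postbaseline visit date". Its denominator likewise requires all the relevant tests on one date. Subjects who meet any one criterion are also listed.

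The protocol's corresponding laboratory criterion (3.4.2) is AST or ALT above "3xULN with at least 1 total bilirubin value" above 2xULN. That line says nothing about dates.

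**The concern.** There are two separate matters.

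First, the data rule for the liver table uses a term that excludes placebo elsewhere in the SAP. A programmer who applies it as written would leave the placebo column empty for the randomised comparison. Liver transaminase elevation is an adverse event of special interest (SAP 7.1.7). Methotrexate and leflunomide are both permitted background drugs, though not together (Protocol 5.8), and that section itself warns about hepatotoxicity with methotrexate. Liver values on three investigational drugs therefore need the concurrent placebo arm beside them.

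Second, the composite is the only joint transaminase–bilirubin count in the SAP. If bilirubin rises after transaminases have already fallen, the subject meets each limit but not on the same date, and is missing from that count.

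**Working it through.** No stated figure in the plan bears on this point, so the check compares texts and adds one worked example.

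**1. What active treatment means in the SAP**

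- 3.8.1: for re-randomised placebo subjects, the on-active-treatment study day starts at the first dose of active drug.
- 4.2.1: for subjects first randomised to placebo, duration of active treatment starts on the first day of active drug.
- 7.1.5.1: active-treatment TEAEs follow the entire-study definition "except that active study drug instead of any study drug will be used".
- 7.1.6: the placebo-controlled period and the active treatment period have separate tables.
- 7.2 and 7.2.2.1: the active treatment period has its own baseline.

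The usage is consistent: placebo is not active treatment.

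**2. Consequence of the literal reading**

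The planned placebo arm is 35 (Protocol 3.2). No placebo subject takes active drug before Week 24, so 0 of 35 contribute to the placebo-controlled column. The seventh group in SAP Table 1, placebo subjects who never start the drug assigned at Week 24, is also empty in the entire-study table.

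**3. Text pointing the other way**

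- 7.2.3 presents the placebo-controlled period (quoted above).
- 7.2.3 opens by covering abnormalities after the first study drug dose, with no active-only limit, and its denominator is drawn from the Safety Analysis Set.
- The general laboratory rule in 7.2 carries no such limit either: summaries "will include data collected up to the last dose of study drug plus 30 days for subjects who have permanently discontinued study drug".

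Nothing in 7.2.3 says which sentence governs.

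**4. The same-date rule, on a hypothetical subject (assumed values)**

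| Date | ALT (xULN) | Bilirubin (xULN) | ALT >3 | Bilirubin >2 | Both |
|---|---|---|---|---|---|
| Week 4 | 4.2 | 1.2 | yes | no | no |
| 5 days later | 2.8 | 2.3 | no | yes | no |

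- Same-date rule: not counted. The result is the same at the 1.5xULN limit, because 1.2 is below 1.5.
- Any-date rule: counted, since the highest ALT is 4.2 and the highest bilirubin is 2.3.
- The subject still appears in the ALT >3xULN row, the bilirubin >2xULN row and the listing. This takes all postbaseline visits to include unscheduled ones.
- Had ALT still been above 3xULN at the second date, the same-date rule would have counted the subject.

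Five days lies within the 3 to 7 day retest span of Protocol 3.4.2, although the first row alone would not trigger that retest unless INR were raised. The result is unchanged if the second values come from the scheduled Week 8 visit, 28 days later.

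**5. Spacing of liver tests**

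Chemistry is scheduled at Day 1 and Weeks 2, 4, 8, 12, 18, 24, 26, 28, 32, 36, 42 and 48. The gaps are 2, 2, 4, 4, 6 and 6 weeks in each 24-week half, or 14, 28 and 42 days. A non-concurrent pattern can therefore arise between scheduled visits as well as at retests.

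**6. Size**

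The documents give no rate of non-concurrent elevations, so no expected number of uncounted subjects can be computed. For scale, one subject in an arm of 35 is 1/35 = 2.9%.

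**The case against.** The strongest reply on the first matter is that the surrounding text shows the intention. A table presented for the placebo-controlled period, by groups that include Placebo, cannot sensibly have an empty placebo column. Nor would the placebo comparison of liver tests be lost. AST, ALT, alkaline phosphatase and bilirubin are summarised by group and visit (SAP 7.2.1), graded abnormalities are shown for the placebo-controlled period (7.2.2.3), and grade shifts are shown to Weeks 12 and 24 (7.2.4). A reader might infer that the plan removes the placebo comparator from its liver safety analysis. The documents do not support that: removal is one of two incompatible readings of one table. What stands is that the data rule, taken as written, contradicts the table it governs.

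On the second matter, requiring both elevations on one date is a defensible choice that trades sensitivity for specificity. Protocol 3.4.2 is a study drug discontinuation criterion. No document says the table must reproduce it, and its silence on timing does not establish an any-date rule. The reply is sound, and it is a reason to keep the same-date row. It does not supply a joint count for the non-concurrent pattern.

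A reader might also infer that any bilirubin rise one visit after a transaminase peak goes uncounted, or that serious liver cases are hidden. Neither follows. The rule needs transaminases above 3xULN on the date of the bilirubin value, not at their peak, and subjects missed by the composite remain in the single-test rows and the listing.

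**Conclusion.** Both points hold in limited form.

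- **Data rule.** SAP 7.2.3 contradicts itself and SAP 3.2 on whether placebo visits enter the placebo-controlled liver table. Read literally, 0 of 35 planned placebo subjects contribute to Weeks 0 to 24; read with its context, all with postbaseline values do. The text should not leave this to the programmer.
- **Composite.** The same-date count is narrower than the protocol's wording. It omits a subject whose transaminases have fallen to 3xULN or below by the time bilirubin rises, unless both limits are met together on some other date. The omission is confined to the composite row, and its frequency cannot be estimated from the documents.

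Both concern descriptive tables without formal testing (SAP 7.2). They merit correction because the changes are small and the by-arm liver comparison is worth protecting. The conclusion rests on the SAP's consistent use of active treatment to exclude placebo. It implies nothing about how subjects should be managed.

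**What to change.** **Placebo-controlled table.** Replace the active-treatment wording with study drug (active or placebo). Keep data up to 30 days after the last dose for subjects who stop, in line with the rule for this period in SAP 7.2.2.1.

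**Entire-study table.** Keep the data of the placebo group that never switched. For subjects re-randomised at Week 24, count or label placebo-period and active-period data separately. Simply substituting study drug here would put elevations that occurred on placebo into the Placebo/Filgotinib, Placebo/Lanraplenib and Placebo/Tirabrutinib columns.

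**Composite.** Keep the same-date row. Add one supplementary row counting subjects with bilirubin above the limit on the date of the transaminase elevation or within a prespecified window after it, up to last dose plus 30 days. The denominator is subjects with any postbaseline AST or ALT and any postbaseline bilirubin. It should differ little from the present one, because these tests share a chemistry panel (Protocol Appendix 6).

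A window of 30 days is an assumption, not a figure from the documents. On nominal visit days, 14 days reaches the next scheduled visit only across the 2-week gaps, 30 days also covers the 4-week gaps, and 42 days covers every gap. Visit windows can stretch each gap by several days. Some limit is needed; without one, a Week 2 ALT could pair with a Week 48 bilirubin.

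**Cost.** A reworded data rule, separate handling of switched subjects in one table, and one extra row. The wider row may include some unrelated bilirubin rises, which the planned listing lets readers check.

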7.2.4. Shifts Relative to the Baseline Value

Shift tables will be presented for change in severity grade from baseline to Week 12 and Week 24.

7.3. Body Weight and Vital Signs

Descriptive statistics will be provided by treatment group for body weight, BMI and vital signs (pulse rate, systolic and diastolic blood pressure, body temperature, and respiratory rate) as follows:

- Baseline value
- Values at each postbaseline visit
- Change from baseline at each postbaseline visit

A baseline value will be defined as the last available value collected on or prior to the date of first dose of study drug. Change from baseline to a postbaseline visit will be defined as the postbaseline value minus the baseline value. Body weight and vital signs measured at unscheduled visits will be included for the baseline value selection.

In the case of multiple values at the visit, data will be selected for analysis as described in Section 3.8.3. No formal statistical testing is planned.

A by-subject listing of vital signs will be provided by subject ID number and visit in chronological order. Body weight and BMI will be included in the vital signs listing, if space permits. If not, they will be provided separately.

7.4. Prior and Concomitant Medications

Medications collected at screening and during the study will be coded using the current version of the Gilead-modified World Health Organization (WHO) Drug dictionary.

The presentations of prior and concomitant medications are described below. In addition, prior and concomitant medication for SjS, SLE and RA will be presented in a separate summary table by medication category (systemic corticosteroids, other corticosteroids, csDMARDs, anti-malarial DMARDs, biologic DMARDs, NSAIDs, other) and preferred term.

All prior and concomitant medications will be provided in a by-subject listing sorted by subject ID number and administration date in chronological order based on Safety Analysis Set.

7.4.1. Prior Medications

Prior medications are defined as any medications taken before a subject took the first study drug (stop date is prior to Day 1).

Prior medications will be summarized by each Anatomical Therapeutic Chemical (ATC) drug class level 2 and preferred name using the number and percentage of subjects for each treatment group and overall. A subject reporting the same medication more than once will be counted only once when calculating the number and percentage of subjects who received that medication. The summary will be ordered alphabetically by preferred term in order of descending overall

frequency. For drugs with the same frequency, sorting will be done alphabetically. For the purposes of analysis, any medication with a stop date prior to the first dosing date of study drug will be included in the prior medication. If a partial stop date is entered the medication will be considered prior unless the month and year (if day is missing) or year (if day and month are missing) of the stop date are after the first dosing date.

Summaries will be based on the Safety Analysis Set. No formal statistical testing is planned.

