7.1.5.2. Incomplete Dates

If the onset date of the AE is incomplete and the AE stop date is not prior to the first dosing date of study drug, then the month and year (or year alone if month is not recorded) of onset determine whether an AE is treatment emergent. The event is considered treatment emergent if both of the following 2 criteria are met:

- The AE onset is the same as or after the month and year (or year) of the first dosing date of study drug, and
- The AE onset date is the same as or before the month and year (or year) of the date corresponding to 30 days after the date of the last dose of study drug

An AE with completely missing onset and stop dates, or with the onset date missing and a stop date later than the first dosing date of study drug, will be considered to be treatment emergent. In addition, an AE with the onset date missing and incomplete stop date with the same or later month and year (or year alone if month is not recorded) as the first dosing date of study drug will be considered treatment emergent.

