7.4.2. Concomitant Medications

Concomitant medications are defined as medications taken while a subject is on study drug, regardless of when the medication was started. Use of general and disease-specific concomitant medications will be summarized by preferred name using the number and percentage of subjects for each treatment group. A subject reporting the same medication more than once will be counted only once when calculating the number and percentage of subjects who received that medication. The summary will be ordered alphabetically by preferred term in descending overall frequency. For drugs with the same frequency, sorting will be done alphabetically.

For the purposes of analysis, any medications with a start date prior to or on the first dosing date of study drug and continued to be taken after the first dosing date, or started after the first dosing date but prior to or on the last dosing date of study drug will be considered concomitant medications. Medications started and stopped on the same day as the first dosing date or the last dosing date of study drug will also be considered concomitant. Medications with a stop date prior to the date of first dosing date of study drug or a start date after the last dosing date of study drug will be excluded from the concomitant medication summary. If a partial stop date is entered, any medication with the month and year (if day is missing) or year (if day and month are missing) prior to the date of first study drug administration will be excluded from the concomitant medication summary. If a partial start date is entered, any medication with the month and year (if day is missing) or year (if day and month are missing) after the study drug stop date will be excluded from the concomitant medication summary.

Medications with completely missing start and stop dates will be listed but not included in the concomitant medication summary, unless the medication is reported as ongoing.

In addition, prior and concomitant medications for SjS, SLE and RA will be presented in a separate summary table by medication category (csDMARD, systemic corticosteroids, other corticosteroids, NSAIDs, anti-malarial drugs and other), and preferred term.

All prior and concomitant medications (other than per-protocol study drugs) will be provided in a by-subject listing sorted by subject ID number and administration date in chronological order based on Safety Analysis Set.

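### SAP 7.4.1 ignores the start date when the stop date is partial, so a drug known to have begun on study can be counted as a prior medication

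*SAP*

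**What the plan says.** SAP 3.6.1 refers the handling of missing medication dates to Section 7.4, so the rules there are the only ones that apply.

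SAP 7.4.1 opens with a definition: "Prior medications are defined as any medications taken before a subject took the first study drug (stop date is prior to Day 1"). For complete dates the working rule follows it: "any medication with a stop date prior to the first dosing date of study drug will be included in the prior medication". For incomplete stop dates, prior is the default: "If a partial stop date is entered the medication will be considered prior unless the month and year (if day is missing) or year". The sole exception is a recorded stop month, or a stop year where nothing finer is known, that comes later than first dosing. The only comparison is between the stop date and first dosing. None of the working rules in 7.4.1 mentions a start date.

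SAP 7.4.2 does use the start date. A drug "started after the first dosing date but prior to or on the last dosing date of study drug will be considered concomitant medications". It drops a partial stop date from the concomitant summary only when that month or year precedes first dosing.

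**The concern.** A stop month or year equal to that of first dosing is not after it, so the exception in 7.4.1 does not apply and the record is prior by default. That is a reasonable convention when the drug began before the study and only its end is unclear. It is not reasonable when the recorded start date shows that the drug began on or after Day 1, because such a drug cannot have been taken beforehand. The section's working rule then gives a result that its own definition rules out.

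At stake is the accuracy of the prior-medication summary, which is shown by treatment group and overall. The false entries come from on-study drug use, which may differ between arms, so they need not be balanced. With about 35 subjects per arm (SAP 1.3), one false entry moves a percentage by 1/35, or 2.9 points.

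**Working it through.** The plan states no figure that depends on this rule, so there is none to reproduce. The check has two parts.

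**1. Apply the rules literally to test records.** Assume first dosing on 10 May 2018 and 336 days of dosing (SAP 4.2.2.1: 7 × 48). The last column adds the condition that the start date precedes first dosing.

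| Record | Start | Stop as recorded | 7.4.1 | 7.4.2 | 7.4.1 with start-date condition |
|---|---|---|---|---|---|
| a | 14 May 2018 | 24 May 2018 | not prior | concomitant | not prior |
| b | 14 May 2018 | May 2018 | **prior** | concomitant | not prior |
| c | 14 May 2018 | June 2018 | not prior | concomitant | not prior |
| d | 1 Sep 2018 | 2018 | **prior** | concomitant | not prior |
| e | 1 Sep 2018 | 2019 | not prior | concomitant | not prior |
| f | 1 Apr 2018 | May 2018 | prior | concomitant | prior |

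Records a and b can be the same drug. Losing the day of the stop date is enough to make it prior. Records b and d are wrong and appear in both summaries. Records c and e show that later partial dates are handled correctly. Record f began before the study and has an ambiguous stop; it stays in the prior summary with or without the added condition.

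**2. How wide the affected window is.** Assume first-dose dates spread evenly over a 365-day year. For each date, count the on-study days that share its calendar month (or year) and divide by 336.

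- Day missing: in a month of L days, the affected days run from 1 to L, counting Day 1, and sum to L(L+1)/2. Over the year: 7 × 496 + 4 × 465 + 406 = 5,738. Mean 5,738/365 = 15.7 days, and 15.7/336 = 4.7%. Range 1/336 = 0.3% to 31/336 = 9.2%.
- Day and month missing: the days left in the year run from 1 to 365, capped at 336. Sum = 336 × 337/2 + 29 × 336 = 56,616 + 9,744 = 66,360. Mean 66,360/365 = 181.8 days, and 181.8/336 = 54%. Range 0.3% to 100%.

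These are shares of possible on-study stop days, given that the stop date is partial. They are not rates of misclassified medications, because the documents do not give the frequency of partial dates.

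**The case against.** The best defence is that the opening definition already acts as a gate: a drug begun after Day 1 was not taken before the first study drug, and the partial-date sentence only settles an uncertain stop. That reading is possible, but the sentence gives the classification outright with one exception, and a programmer would code it that way. At best the section contradicts itself.

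The defence on consequences is stronger, and most of it stands.

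- A reader might infer that rescue or newly started treatment would be hidden. It would not: the record stays in the concomitant summary and in the by-subject listing (SAP 7.4, 7.4.2).
- A reader might infer a spurious baseline imbalance in steroid or DMARD use. SAP 5.2 defines these characteristics separately, as concurrent use at baseline, and SAP 3.3 does the same for the stratification factor. Neither is stated to come from the prior-medication table.
- A reader might infer that the SjS/SLE/RA table is distorted. SAP 7.4 and 7.4.2 describe it as covering prior and concomitant medication by category, and do not say that it separates the two.
- Each subject counts once per medication, so nothing changes if the same drug was also taken and stopped before Day 1.
- Year-only stop dates should be uncommon for on-study drugs: source records must carry start and end dates (Protocol 9.1.5), and data entries are monitored and queried (Protocol 9.1.6). Partial dates are more plausible for old SjS treatment, all of which is recorded at screening (Protocol 6.2.1). A prior default suits those records.

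A reader might also object that a drug with both dates missing is listed but not summarised as concomitant ("Medications with completely missing start and stop dates will be listed but not included in the concomitant medication summary", unless ongoing), while an adverse event with both dates missing counts as treatment emergent (7.1.5.2). Counting undated events is a cautious safety convention. Nothing in the documents requires medication tables to follow it, so the difference is a matter of preference and not an error.

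**Conclusion.** Wrong as written, and minor. Under SAP 7.4.1, a medication with a known start on or after Day 1 is counted as prior whenever its partial stop date falls in the month (day missing) or year (day and month missing) of first dosing. The same record is counted as concomitant under 7.4.2.

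The effect is limited to false extra entries in the descriptive prior-medication summary, for which no formal testing is planned. Nothing in the visible text ties an efficacy test, stratum, estimand or baseline variable to this rule. The size in practice is unknown. The average window of about 5% of on-study days for day-missing stops, or about 54% for year-only stops, rests on the assumption of evenly spread first-dose dates. The documents do not support a claim that a given share of all partial-date records is misclassified: a drug stopped in an earlier year, for example, is certainly prior.

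**What to change.** Add a start-date condition to the partial-stop sentence in SAP 7.4.1: the medication is prior only if, in addition, the start date is before the first dosing date, or is missing or partial and not after it. A medication known to have started on or after Day 1 is then concomitant only. Records with a pre-study or unknown start and an ambiguous stop stay in the prior summary as now.

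Do not go further and require the latest possible stop date to precede Day 1. That would remove true pre-study treatment from the prior table. For example, a biologic started in 2015, with its stop recorded only as 2018 and first dosing in September 2018, would be lost from treatment history.

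The cost is one clause in the SAP and one condition in the derivation. Design, data collection and power are unaffected.
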